# 2. AIMS AND OBJECTIVES

The aim of UNiTY is to investigate the clinical and cost-effectiveness of up to three cycles of IUI versus one cycle of IVF in couples with UEI.

# 2.1. Internal pilot objectives

The trial includes an internal pilot phase to assess feasibility and acceptability. The decision to continue to a full trial will be based on pre-defined stop-go criteria (see Table 1), and informed by the findings from the pilot qualitative process evaluation (QPE).

The pilot objectives for the trial are:

- To assess the feasibility of recruitment to the UNiTY trial [MRC/NIHR framework, core element 4 & 5: uncertainties & refinement]
- To assess the feasibility of opening fertility centres to the UNiTY trial
- To explore and understand the feasibility, acceptability, ethical implications and context of the UNiTY trial interventions with couples and healthcare professionals (HCPs) [MRC/NIHR framework, core elements 1-6: context, programme theory, stakeholders, uncertainties, refinement & economic considerations].

# 2.2. Main trial objectives

### 2.2.1. Clinical aims and objectives

The primary objective is to test the hypothesis that in couples with UEI, the policy of offering three cycles of IUI is not substantially worse than the policy of offering IVF by up to a 10% margin of non-inferiority in terms of live birth \ge 34 weeks [MRC/NIHR framework, core element 4: uncertainties].

The secondary clinical objectives for the trial are:

- 1. To evaluate the rates of pregnancy loss for IUI versus IVF for couples with UEI.
- 2. To compare the health of babies born as a result of IUI versus IVF to couples with UEI.
- 3. To compare the complication rates of the two treatment arms.
- 4. To evaluate the TTP leading to a live birth for IUI versus IVF for couples with UEI.
- 5. To explore patient satisfaction in the two treatment arms.
- 6. To compare outcomes of couples over a longer period of 25 months post-randomisation when further interventions may have been provided.
- 7. To explore the different clinical features of IUI and IVF cycles.
- 8. To explore the reasons patients may not complete the full course of treatment or wish for different treatment options.

### 2.2.2. Economic aims and objectives

The health economics analysis within UNITY aims to evaluate the cost effectiveness of up to three cycles of IUI compared to one cycle of IVF for couples with UEI. [MRC/NIHR framework, core element 6: economic considerations].

### 2.2.3. Healthcare Science aims and objectives

The embedded healthcare science work will investigate the variations in how male factors in infertility are assessed across the clinical partners involved in the trial. A quality assurance check for the sperm analysis performed prior to entry in the trial will be provided. Further, the prognostic value of both existing (WHO), and novel (including flagellar beat) markers for male factor infertility will be evaluated

in relation to treatment outcomes for both IUI and IVF. [MRC/NIHR framework, core element 4: uncertainties].

# 2.2.4. Bioethics aims and objectives

The Qualitative Process Evaluation will help inform the ethical issues that will be explored in greater depth as part of the bioethics sub-study. Interviews will be carried out with trial participants (who have completed treatment), clinicians and commissioners to explore the intersection between costs of treatment and treatment choices. The bioethics sub-study aims to understand the perspectives of clinicians, commissioners and patients [MRC/NIHR framework, core element 1, 3 & 4: context, stakeholders & uncertainties].

# 2.2.5. Patient Reported Outcomes Objectives

- Health related quality of life (HRQoL) (using the EQ-5D-5L overall score and thermometer scale) measured at baseline, and 9 and 19 months post randomisation, plus 25 months for couples who conceive within 450 days of randomisation;
- Satisfaction with treatment and care provision (using the CSQ-8 [36]) post-treatment.

\_\_\_\_\_

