### **Patient reported outcomes**

- Health related quality of life (using the EQ-5D-5L questionnaire overall score and thermometer scale (36)) measured at baseline, during the first treatment cycle\* of IUI and/or IVF, and 19 months post randomisation (and 25 months for couples who conceive within 450 days of randomisation);
- Satisfaction with treatment and care provision (using the CSQ-8 (37)) measured during the first treatment cycle\* of IUI and/or IVF, and 19 months post randomisation (and 25 months for couples who conceive within 450 days of randomisation).

Consent will be taken from couples to allow longer-term assessment of pregnancy and live birth rate through routine data sources. Funding to carry out this work through to 5 years post-randomisation will be requested through a separate application.

\*The ideal timepoint during a treatment cycle to collect these questionnaires is between the date of insemination and the date of the pregnancy test for couples undergoing IUI, and between the date of embryo transfer and the date of the pregnancy test for couples undergoing IVF.

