## Additional notes on Error! Reference source not found.

- Months 2-6 are an approximation for when couples will have the three cycles of IUI; this process may be longer.
- X Couples randomised to IUI but progress to IVF as part of clinical care. All couples randomised to IUI cannot progress to subsequent IVF treatment until 270 days (approximately 9 months) post randomisation.
- X to measure outcomes for all couples who conceive within 450 days of randomisation.
- X³- one Clinical Pregnancy Outcome CRF to be completed per positive pregnancy test.
- X- to be completed for each pregnancy conceived during the trial outside of IVF or IUI treatment.
- X one Post-Treatment CRF to be completed 8 weeks after treatment starts (defined as the first day of ovarian stimulation).
- The qualitative sub-studies will approach participants at the indicated timepoints, but their interviews will happen in the subsequent weeks.
- X- measured during the first treatment cycle of IUI and/or IVF. The ideal timepoint during a treatment cycle to collect these questionnaires is between the date of insemination and the date of the pregnancy test for couples undergoing IUI, and between the date of embryo transfer and the date of the pregnancy test for couples undergoing IVF.

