11.2. Case Report Form (CRF) completion

The CRFs will include (but will NOT be limited to) the Forms shown in **Error! Reference source not found.** 

**Table 6**: Case report forms in UNiTY

Form Name	Schedule for submission
Informed Consent Form (one for each partner)	Prior to randomisation
Screening CRF	Prior to randomisation
Baseline CRF	Prior to randomisation
Baseline participant questionnaire: - EQ-5D-5L	Prior to randomisation
Treatment CRFs: - IVF treatment CRF - IUI treatment CRF - Laboratory CRF - Frozen Transfer CRF	During or as soon as possible after treatment
Outcomes CRF: - Post-treatment CRF	8 weeks after treatment starts (defined as the first day of ovarian stimulation) in order to capture all potential complications/outcomes.
Outcomes CRF: - Clinical Pregnancy outcome CRF	As soon as possible after each follow up assessment time point (19 months and 25 months post randomisation)
Outcome participant questionnaires  - EQ-5D-5L (one questionnaire to be completed for each partner)  - CSQ-8 (one questionnaire to be completed for each partner)  - Health resource use (one questionnaire to be completed per couple)	As soon as possible after each follow up assessment time point (during the first treatment cycle of IUI and/or IVF, 19 months and 25 months post randomisation)
Non-trial treatment form	During or as soon as possible after treatment
Natural pregnancy notification CRF	As soon as possible after becoming aware of participant's pregnancy
Serious Adverse Event Form	If expedited: emailed within 24 hours of site research team becoming aware of event If non-expedited: emailed within 4 weeks of site research team becoming aware of event
Change of Status Form	As soon as possible after the point of reduced participation
Deviation Form	As soon as possible after a protocol deviation has occurred

A CRF should be completed for each couple or individual participant as documented at the top of each document. CRFs repeat to account for multiple treatment cycles and multiple pregnancies.

In all cases it remains the responsibility of the PI to ensure that the CRF has been completed correctly and that the data are accurate. This will be evidenced by the signature of the PI, or delegate(s). The Site Signature & Delegation Log will identify all those personnel with responsibilities for data collection.

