#### 15.1. Economic data collection

The economic analysis will be conducted from the perspective of the health care system, accounting for the direct costs incurred by the UK NHS as recommended by NICE (42), including individual level data on all health-related resource use. The main resource categories that will be monitored include the following:

- 1. Drug administration
- 2. Resource use of standard care
- 3. Resource use associated with adverse events and complications (including premature birth and neonatal care)
- 4. Resource use associated with outpatient or emergency visits and hospital admissions
- 5. Contacts with community and social care services, such as general practitioner, practice nurse and counsellors

To estimate the overall cost of each trial-arm, unit costs will be applied and attached to each resource item. Information on unit costs will be obtained from centres participating in the trial and UK national sources such as NHS Reference Costs (39), Unit Costs of Health and Social Care (43), the British National Formulary (BNF), and Office for National Statistics (ONS). Costs used in other relevant published sources will be sought for use in sensitivity analysis.

HrQoL data will also be obtained based on participants' responses to the EQ-5D-5L. A preference-based index of HrQoL will be derived using the recently published English value set, and QALYs will be calculated using the area under the curve approach.

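### The objectives promise a 9-month EQ-5D-5L that the schedule never collects; as scheduled, no questionnaire isolates the IUI policy before follow-on IVF opens, and the number of QALY readings can differ by arm

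*Protocol*

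**What the plan says.** Two sets of timings stand in the protocol.

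- **Section 2.2.5 (objectives).** EQ-5D-5L is "measured at baseline, and 9 and 19 months post randomisation", with a 25-month reading for couples who conceive within 450 days. For CSQ-8 the text is "Satisfaction with treatment and care provision (using the CSQ-8 [36]) post-treatment", with no month given.
- **Section 8.2.2.1 (patient reported outcomes).** EQ-5D-5L is "measured at baseline, during the first treatment cycle" "of IUI and/or IVF, and 19 months post randomisation". CSQ-8 has the same follow-up times without the baseline.
- **Section 9.1, Table 2 and note X6.** EQ-5D-5L, CSQ-8 and Health Resource use are marked at Month 2 and Month 19, and at Month 25 for those who conceive within 450 days. Note X6 explains the Month 2 mark as "measured during the first treatment cycle of IUI and/or IVF". Ideally the form is completed "between the date of insemination and the date of the pregnancy test for couples undergoing IUI", or between embryo transfer and the test for IVF.
- **Section 11.2, Table 6.** The questionnaires are due "during the first treatment cycle of IUI and/or IVF, 19 months and 25 months post randomisation".

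Section 15.1 adds that "QALYs will be calculated using the area under the curve approach".

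**The concern.** The trial compares a policy of three IUI cycles with a policy of one IVF cycle. Note X1 to Table 2 says that IUI-arm couples cannot move to follow-on IVF before day 270. Section 1.1.4 expects all couples unsuccessful after three IUI cycles to go on to at least one IVF cycle. A month-9 questionnaire is therefore the natural place to read quality of life and satisfaction under the two policies before crossover. Section 2.2.5 promises it for EQ-5D-5L, but the operative schedule omits it.

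At stake are secondary objective 5 in Section 2.2.1 (satisfaction in the two arms), the quality-of-life objective and the QALYs. A statistical analysis plan cannot repair this, because a reading that was never collected cannot be recovered.

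**Working it through.** **Step 1: the time points side by side.**

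| Source | EQ-5D-5L | CSQ-8 | Month 9? |
|---|---|---|---|
| 2.2.5 | 0, 9, 19 (25) | post-treatment | EQ-5D-5L yes |
| 8.2.2.1 | 0, first cycle, 19 (25) | first cycle, 19 (25) | no |
| 9.1 Table 2, note X6 | 0, first cycle (Month 2), 19 (25) | first cycle (Month 2), 19 (25) | no |
| 11.2 Table 6 | baseline, first cycle, 19, 25 | first cycle, 19, 25 | no |

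Three places agree with one another and differ from Section 2.2.5.

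**Step 2: what each scheduled reading covers.**

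- *First cycle.* In the IVF arm the ideal window opens after embryo transfer, when essentially the whole allocation has been delivered. In the IUI arm it opens after insemination 1 of up to 3.
- *19 months.* This is the next time common to both arms. By then, IUI-arm couples who were unsuccessful have had about 10 months (month 9 to month 19) in which follow-on IVF was open to them.
- *Between the two.* No reading is scheduled for all couples.

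**Step 3: the number of readings.** The wording in 8.2.2.1, note X6 and Table 6 covers the first cycle of IUI and/or IVF. An IUI-arm couple that crosses over may therefore complete a second in-cycle form at its first IVF. Table 2 does not settle this: the follow-on IVF Treatment CRF is marked at Month 9 (note X1), but X6 appears only at Month 2.

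**Step 4: effect on the area under the curve.** Under the trapezoid rule an interior reading has weight (next time − previous time)/2. The first and last readings have half the adjacent interval. In months, over 0 to 19:

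- Times 0, 2, 19: baseline 2/2 = 1.0; first cycle (19 − 0)/2 = 9.5; month 19 (19 − 2)/2 = 8.5. The first-cycle share is 9.5/19 = 50%.
- Times 0, 2, 10, 19 (month 10 is an assumption): baseline 1.0; first cycle (10 − 0)/2 = 5.0; second in-cycle (19 − 2)/2 = 8.5; month 19 (19 − 10)/2 = 4.5. The two in-cycle readings together carry 13.5/19 = 71%.
- Range: with the second reading at month t, the first-cycle weight is t/2. It is 4.5 at month 9 and about 7.4 at day 450 (450/30.4375 = 14.8 months). Taking day 450 as the upper end is also an assumption, since the protocol sets no limit for this form.
- Times 0, 9, 19 (Section 2.2.5): 4.5, 9.5, 5.0.

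The first-cycle reading thus carries 9.5 months for a couple with one in-cycle form. It carries roughly 4.5 to 7.4 months for a couple with two, and the second form goes to IUI-arm couples who were unsuccessful.

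**The case against.** The strongest reply is that Section 2.2.5 is simply stale text. The other three places agree, and 2.2.5 cites CSQ-8 as reference 36, whereas Section 8.2.2.1 and the reference list give 36 for EQ-5D-5L and 37 for CSQ-8. On that view the remedy is to correct one line. This may well be so, but it leaves the schedule's own gap and the unequal number of readings in place.

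Several stronger readings might be inferred and are not supported:

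- *That the allocated treatments are not measured at all.* EQ-5D-5L and CSQ-8 are collected in the first cycle and again at 19 months, and the first-cycle form catches both arms at the same procedural stage.
- *That the CSQ-8 objective is flatly contradicted.* The 19-month CSQ-8 is literally post-treatment. The difficulty is that in the IUI arm it may reflect IUI plus later IVF.
- *That resource use is recalled over about 17 months.* The questionnaire's recall period is not stated, Section 2.2.5 does not mention resource use, and treatment, complication and non-trial treatment forms capture part of it.
- *That the cost-effectiveness result is undermined.* Section 15.3 reports QALYs separately, to convey the impact of the treatment process, and does not expect a cost-per-QALY analysis.

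Two points against a month-9 reading stand in part. On times 0, 9 and 19 a single reading still carries 9.5 of 19 months, so the gain is a common time in both arms and not a lighter weight. Day 270 is also not the end of IUI for everyone, since cycle timing is left to the couple and Section 7.1.1 allows cycles up to day 450.

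**Conclusion.** The point holds in a limited form. Section 2.2.5 contradicts Sections 8.2.2.1, 9.1 and 11.2 on the 9-month EQ-5D-5L. As scheduled, no questionnaire isolates the IUI policy before follow-on IVF opens. If crossover couples complete a second in-cycle form, the weight of the first-cycle EQ-5D-5L falls from 9.5 months to 5.0 (second form at month 10), so it depends on arm and outcome.

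The size of any resulting QALY bias cannot be given, because the protocol states no utility values. The weights assume a first cycle at month 2, as Table 2 places it, and use of every available reading in the area under the curve. The day-270 boundary is taken from note X1. Section 7.1.1 (three cycles or 270 days) and Section 15.2 (eight months) word it differently and should be reconciled with that note.

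The consequences are confined to secondary outcomes, which Section 14.2 treats as exploratory, and to separately reported QALYs. The primary outcome and the effect measure in cost per live birth are untouched. The change is still worth making, because it is cheap and the missing data could not be recovered.

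**What to change.** 1. Reconcile Section 2.2.5 with Section 8.2.2.1, Table 2 and Table 6. Preferably add EQ-5D-5L and CSQ-8 at month 9 (day 270) for all couples in both arms, whatever their treatment stage.
2. State that the between-arm QALY comparison uses time points common to both arms (0, 9 and 19 months if the form is added). Keep the follow-on IVF in-cycle reading out of it, and report in-cycle readings as process measures.
3. Say whether IUI and/or IVF means a second in-cycle form after crossover, and show X6 in Table 2 wherever it applies.
4. If the month-9 form is not added, delete it from Section 2.2.5. State that the 19-month comparison reflects IUI plus any later IVF, and still exclude the second in-cycle reading from the between-arm QALY.

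Cost: one extra online form per partner, at most 942 × 2 = 1,884 forms, plus the wording changes. Some couples will still be in IUI treatment at day 270, so treatment stage at completion should be recorded and reported.

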# 3. TRIAL DESIGN AND SETTING

### 3.1. Trial design

UNITY is a parallel, open, multicentre, non-inferiority RCT with integrated economic, healthcare science and bioethics evaluations. It includes an internal pilot phase (9 months) with embedded qualitative process evaluation.

### 3.2. Trial setting

The trial will take place in HFEA licenced fertility treatment centres in the UK. These may be NHS or private providers carrying out NHS funded treatments. Self-funded patients at these sites will be included where providers have suitable indemnity for this in place as determined by the Sponsor.

#### 3.3. Sub-studies

Three sub-studies are included in the UNiTY trial. Please refer to section 16 for detailed information.

#### Qualitative process evaluation

A pragmatic qualitative process evaluation embedded in the pilot phase will explore and understand the feasibility, acceptability, ethical implications and context of the intervention, as well as the evaluation design, with couples and HCPs. In addition, it will explore ethical acceptability, potential health equity and equality concerns regarding access to the trial. The results will dynamically inform decision-making around progression to the full trial and the bioethics sub-study.

#### **Healthcare science**

Accurate diagnosis of the partner providing sperm is a key factor in diagnosing UEI and assessing suitability for IUI. UNITY will investigate the variations in male factor assessments across the centres taking part in the trial, and assess and moderate the clinical investigations done prior to trial entry. There will also be a mechanistic investigation of whether these measures can be improved in the future through the use of novel sperm-imaging to predict outcomes.

#### **Bioethics**

Embedded within the main trial, this bioethics evaluation using qualitative methods explores further ethical issues with couples who have completed the trial protocol. Building on the process evaluation, interviews will gather the reflections of participants, clinicians and commissioners on the trial processes, and will explore potential health equity and equality concerns regarding access to the trial and the proposed intervention.

#### 3.4. Assessment of risk

All clinical trials can be considered to involve an element of risk and in accordance with the Birmingham Clinical Trials Unit (BCTU) standard operating procedures this trial has been risk assessed to clarify any risks relating uniquely to this trial beyond that associated with usual care. A Risk Assessment has been conducted and concluded that this trial corresponds to the following categorisation: No higher than the risk of standard medical care.

### 3.5. Patient and public involvement

Section 1.1.5 details the involvement patients and the public have had in the design of the trial.

Beyond this, the trial team will include PPI representatives throughout the trial, ensuring representation from a range of backgrounds. Individuals will review participant-facing documents, and sit on committees. A PPI panel will be convened to review the trial as it progresses and advise the trial team.

As well as the usual benefits for PPI participation, counselling will be available in the event that the discussion of infertility and fertility treatment is more difficult than anticipated for contributors.

# 4. ELIGIBILITY

#### 4.1. Inclusion criteria

Couples with a diagnosis of UEI, referred to fertility centres for assisted conception, will be considered for the UNITY trial.

Unexplained infertility for the purpose of this trial is defined as the absence of the following after complete investigations:

- Partner providing eggs infertility due to:
  - o Tubal disease
  - Deep endometriosis +/- ovarian endometriosis
  - Significant uterine abnormality requiring surgery (including cavity distorting fibroids, fibroids >5cm or multiple fibroids)
  - Uterine septum with history of previous pregnancy loss
- Partner providing sperm infertility due to:
  - o Total progressively motile sperm count ≤10Million
  - Normal sperm morphology of ≤2%\*

# 4.2. Exclusion criteria

- Partner providing eggs is 39 years or older on the date of randomisation
- Either partner is under 18 years old on the date of consent
- Partner providing eggs body mass index (BMI) is <19.0 or >34.9 kg/m^2
- Either or both partners have a diagnosis of an ongoing sexually transmitted infection
- Either partner is taking any prohibited medication(s)/intervention(s)
- The couple has two or more consecutive IVF treatment failures
- Either partner unable to provide informed consent
- Either partner unable to complete trial follow-up
- If self-funded, inability to pay for IVF

If couples do not meet the requirements for NHS-funded IVF in their area, but do meet the trial eligibility criteria, they can proceed as self-funded participants.

The age limit for partners providing eggs for NHS-funded IVF treatment is 40 years. In order for couples to have multiple cycles of IUI followed by IVF before turning 40, and without jeopardising their funding, partners providing eggs will need to be <39 years of age on the date of randomisation. Research teams will discuss this with all couples during screening, particularly those in which the partner is close to the age eligibility limit to be sure they understand the possibility of losing NHS funding.

